### 5.1.5. Solicited Local (Injection Site) Reactions

The analysis of local solicited adverse events will include:

1. Pain
2. Erythema
3. Induration

---

4. Swelling
5. Itching
6. Warmth

### 5.1.6. **Solicited Systemic Adverse Events**

The analysis of systemic solicited adverse events will include:

1. Fever (defined as body temperature of 38.0°C or higher)
2. Headache
3. Fatigue
4. Myalgia
5. Nausea
6. Vomiting
7. Arthralgia
8. General Itching
9. Chills
10. Rash

## 5.2. **Clinical Laboratory Tests**

The data will be summarized by the type of laboratory test.

In case a laboratory test result is *censored* (no numeric value is available, but only a verbatim term) then a numeric value will be imputed by a value preceding or exceeding the cut-off value with one unit. (<x: subtract 1 unit from x, >x: add 1 unit to x)

*Toxicity grades* will be determined according to the DAIDS Grading list (See also Appendix 1). In case no toxicity grades are defined for a test, the abnormalities (above/below normal range) will be used. In determining toxicity grades, the following rules are applied:

- worst grades/abnormalities are determined over the whole observational period for each trial phase separately, including all post-baseline measurements of that phase.
- The abnormalities 'abnormally low' and 'abnormally high' are considered equally important, i.e. if a subject has as well an abnormally low as an abnormally high value post-baseline, both abnormalities are shown in the tables. (This means that the sum of the percentages can be more than 100%)
- Note: as the grading scale for some parameters in the grading table has some gaps (zones where no toxicity grade definition exists), laboratory results falling in these zones will be allocated to the adjacent worst-case grade.
- If a lab value falls within the grading as specified in the grading table but also within the (local) lab normal limits, the value is considered as normal

**Definition emergent:** An abnormality (toxicity grade or abnormality based on normal ranges) will be considered emergent in a particular phase if it is worse than the baseline (baseline = prior very first vaccination). If the baseline is missing, the abnormality is always considered as emergent. A shift from 'abnormally low' at baseline to 'abnormally high' post baseline (or vice versa) is also emergent.

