Laboratory values will be graded according to a modified version of the DAIDS Table for Grading the Severity of Adult and Pediatric Adverse Events (DAIDS AE Grading Table), Version 1.0 dated December 2004 (Clarification, August 2009) included in [Attachment 1](#), and, if clinically significant, reported as AEs.

Additional clinical laboratory assessments to be performed are as follows:

- Serum pregnancy testing (β -hCG) for women of childbearing potential at screening
- Urine pregnancy testing for women of childbearing potential pre-dose on Day 1, Weeks 12, 24, 48, 60, 96 and at the early exit visit. A urine pregnancy test will also be carried out prior to mucosal secretion collection, for those females who have consented to this procedure.
- Troponin at screening
- Serology: hepatitis B, and hepatitis C at screening
- Syphilis, chlamydia, gonorrhea and trichomonas at screening, and additionally at Weeks 2, 14, 26, 50, 60, and 96 for subjects who consent to mucosal secretion collection
- HIV testing at screening, pre-dose on Day 1, Weeks 12, 24, and 48, and additionally at Weeks 78 and 96, at the early exit visit and at each visit of LTE phase.

Electrocardiogram (ECG)

Supine 12-lead ECGs will be performed at screening and at Week 16, and only performed again during the study if clinically indicated based on signs and symptoms.

For 30 minutes prior to the ECG, subjects should refrain from meals, hot or cold beverages and strenuous exercise, and should remain in a room with a comfortable temperature. Each ECG should be obtained after the subject has been at rest for at least 5 minutes. ECG interpretation/comparison will be provided by a central reading cardiologist.

Computer-generated interpretations of ECGs should be reviewed for data integrity, reasonableness and for immediate safety assessment by the investigator or appropriately delegated healthcare provider. Digital ECG data will be transmitted to a centralized ECG over-read service provider. Over-read of the ECGs will be transmitted back to the site within 72 hours. The centralized ECG over-read data will be considered source data.

Vital Signs

Vital sign measurements will be performed at time points specified in the Time and Events Schedule. Blood pressure and pulse/heart rate measurements should be preceded by at least 5 minutes of rest in a quiet setting without distractions.

The following measurements will be performed:

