11.5. Safety Analyses

No formal statistical testing of safety data is planned. Safety data will be analyzed descriptively (including 95% confidence interval).

Baseline for all safety parameters will be defined as the last evaluation done before the first dose of study vaccine.

Adverse Events and Reactogenicity

The verbatim terms used in the CRF by investigators to report AEs will be coded using the Medical Dictionary for Regulatory Activities (MedDRA). All reported AEs (local and systemic, solicited and unsolicited) with onset during the treatment period (ie, treatment-emergent AEs, and AEs that have worsened since baseline) will be included in the analysis. For each AE, the number and percentage of subjects who experience at least one occurrence of the given event will be summarized by group, including exact 95% confidence intervals. Summaries, listings, datasets, or subject narratives may be provided, as appropriate, for those subjects who die, who discontinue vaccinations due to an AE, or who experience a severe AE or an SAE. The analysis for solicited AEs will be done on those subjects in the safety population for whom reactogenicity assessments are available in the database. The analysis of unsolicited AEs will be done based on the safety population.

Clinical Laboratory Tests

Laboratory data will be summarized by type of laboratory test. Descriptive statistics (actual values and changes from reference) will be calculated for each laboratory analyte at baseline and at each scheduled time point. Graphical presentation of changes in laboratory tests will be made as applicable. Baseline refers to the pre-dose value on Day 1. If this value is not available, the value at screening will be used as baseline value. Laboratory abnormalities will be determined according to a modified version of the DAIDS Table for Grading the Severity of Adult and Pediatric Adverse Events (DAIDS AE Grading Table), Version 1.0 dated December 2004 (Clarification, August 2009) included in [Attachment 1](#), and in accordance with the normal ranges of the clinical laboratory. Laboratory abnormalities will be tabulated per treatment group.

Electrocardiogram (ECG)

All statistical analyses of ECG variables will use the centralized ECG over-read data.

The effects on cardiovascular variables will be evaluated by means of descriptive statistics and frequency tabulations.

Vital Signs

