12.1.3. Severity Criteria

All AE and laboratory data will be coded for severity using a modified version of the DAIDS Table for Grading the Severity of Adult and Pediatric Adverse Events (DAIDS AE Grading Table), Version 1.0 dated December 2004 (Clarification, August 2009) included in [Attachment 1](#).

For AEs not identified in the grading table (eg, diagnosis of HIV infection), the following guidelines will be applied:

| | | |
|-----------------|---------|--|
| Mild | Grade 1 | Symptoms causing no or minimal interference with usual social and functional activities |
| Moderate | Grade 2 | Symptoms causing greater than minimal interference with usual social and functional activities |
| Severe | Grade 3 | Symptoms causing inability to perform usual social and functional activities |

| | | |
|-------------------------------------|---------|---|
| Potentially life-threatening | Grade 4 | Symptoms causing inability to perform basic self-care functions OR medical or operative intervention indicated to prevent permanent impairment, persistent disability |
| Fatal | Grade 5 | For any AE where the outcome is death, the severity of the AE is classified as Grade 5 |

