Addendum 3 - Rectal Grading Table for Use in Microbicide Studies - PDF

Grade 5

For any AE where the outcome is death, the severity of the AE is classified as Grade 5.

Estimating Severity Grade for Parameters Not Identified in the Table

In order to grade a clinical AE that is not identified in the DAIDS AE grading table, use the category “Estimating Severity Grade” located on top of the table on Page 96.

Determining Severity Grade for Parameters “Between Grades”

If the severity of a clinical AE could fall under either one of two grades (eg, the severity of an AE could be either Grade 2 or Grade 3), select the higher of the two grades for the AE. **If a laboratory value that is graded as a multiple of the ULN or LLN falls between two grades, select**

the higher of the two grades for the AE. For example, Grade 1 is $2.5 \times \text{ULN}$ and Grade 2 is $2.6 \times \text{ULN}$ for a parameter. If the lab value is $2.53 \times \text{ULN}$ (which is between the two grades), the severity of this AE would be Grade 2, the higher of the two grades.

Values Below Grade 1

Any laboratory value that is between either the LLN or ULN and Grade 1 should not be graded.

Determining Severity Grade when Local Laboratory Normal Values Overlap with Grade 1 Ranges

In these situations, the severity grading is based on the ranges in the DAIDS AE Grading Table, even when there is a reference to the local lab LLN.

For example: Phosphate, Serum, Low, Adult and Pediatric > 14 years (Page 20) Grade 1 range is $2.50 \text{ mg/dL} - < \text{LLN}$. A particular laboratory's normal range for Phosphate is $2.1 - 3.8 \text{ mg/dL}$. A participant's actual lab value is 2.5. In this case, the value of 2.5 exceeds the LLN for the local lab, but will be graded as Grade 1 per DAIDS AE Grading Table.

II. Definitions of terms used in the Table:

| | |
|---|--|
| Basic Self-care Functions | Adult Activities such as bathing, dressing, toileting, transfer/movement, continence, and feeding. |
| | Young Children Activities that are age and culturally appropriate (eg, feeding self with culturally appropriate eating implement). |
| LLN | Lower limit of normal |
| Medical Intervention | Use of pharmacologic or biologic agent(s) for treatment of an AE. |
| NA | Not Applicable |
| Operative Intervention | Surgical OR other invasive mechanical procedures. |
| ULN | Upper limit of normal |

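### SAP 5.2 resets DAIDS-graded laboratory values to normal when they lie within local limits, contrary to the protocol's overlap rule, and declares no departure

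*SAP*

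**What the plan says.** SAP 5.2 (Clinical Laboratory Tests) takes the DAIDS list as the grading standard and then adds a bullet: a value that falls in a grade "but also within the (local) lab normal limits, the value is considered as normal". The bullet is not confined to Grade 1. The same section gives normal ranges a separate job for ungraded tests: "In case no toxicity grades are defined for a test, the abnormalities (above/below normal range) will be used". It also defines emergence, under which an abnormality "will be considered emergent in a particular phase if it is worse than the baseline".

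The protocol makes Attachment 1 the standard for laboratory data in two places. Section 9.3.2: "Laboratory values will be graded according to a modified version of the DAIDS Table". Section 12.1.3: "All AE and laboratory data will be coded for severity using a modified version of the DAIDS Table". Attachment 1 has its own clause for the case where a laboratory's normal limits extend into the lowest grade band: "In these situations, the severity grading is based on the ranges in the DAIDS AE Grading Table, even when there is a reference" (the sentence then names the laboratory's own lower limit). Its example is a serum phosphate with a local range of 2.1 to 3.8 mg/dL: "the value of 2.5 exceeds the LLN for the local lab, but will be graded as Grade 1 per DAIDS AE Grading Table".

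Protocol 11.5 says that laboratory abnormalities are determined by the Attachment 1 table and also "in accordance with the normal ranges of the clinical laboratory".

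**The concern.** The two documents give opposite answers to one question: what to do with a value that meets a DAIDS grade but is normal locally. The SAP presents its tables as DAIDS-graded, so a reader would take them to follow Attachment 1. They do not. For tests with fixed cut-offs, the grade comes to depend on which laboratory ran the sample.

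The worst-grade tables of SAP 5.2.1 can therefore show fewer grades than the protocol's standard would give. SAP 2.4 also plans laboratory subgroups by region and race. Tests are run by local laboratories (protocol 9.3.2), so the same neutrophil count can be Grade 1 in one region and normal in another. SAP 5.1.1 grades adverse events by the protocol's table with no local-limit exception, so one value could be graded in an adverse event table and normal in a laboratory table.

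**Working it through.** **Step 1: apply both rules to the protocol's own example.** Phosphate 2.5 mg/dL, local range 2.1 to 3.8. Attachment 1 gives Grade 1; SAP 5.2 gives normal. The conflict is direct. (Phosphate is measured only at screening under protocol 9.3.2, so the example shows the rule and not a post-baseline effect.)

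**Step 2: which blood tests can be affected.** In SAP Appendix 1, ALT and AST grades start at 1.25 x ULN and creatinine at 1.1 x ULN, so a graded value cannot be within normal limits. Neutrophils (ANC), haemoglobin, platelets and white cells (WBC) have fixed cut-offs and can overlap.

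**Step 3: whether overlap is foreseen.** Protocol 4.1 admits, with approval, ANC of 1,300/mm3 or less if within site ranges, and haemoglobin below 11.0 g/dL if above the site's lower limit (LLN). The ANC Grade 1 band is 1,000 to 1,300 and the haemoglobin band is 10.0 to 10.9. For these two tests the protocol itself expects the overlap. It has no such exception for WBC or platelets.

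**Step 4: share of each Grade 1 band that is reset.** Share = (upper - LLN) / (upper - lower). The bands are from SAP Appendix 1. Every LLN is an assumption. The result is a share of band width, not of subjects.

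| Test | Grade 1 band | All reset at LLN | Part reset | None reset at LLN |
|---|---|---|---|---|
| ANC (10^9/L) | 1.0 to 1.3 | 1.0 | LLN 1.2: (1.3 - 1.2)/0.3 = 33% | above 1.3 |
| WBC (10^9/L) | 2.0 to 2.5 | 2.0 | LLN 2.3: (2.5 - 2.3)/0.5 = 40% | above 2.5 |
| Platelets (10^9/L) | 100 to 124.999 | 100 | LLN 115: (124.999 - 115)/24.999 = 40% | 125 or more |
| Haemoglobin (g/dL) | 10.0 to 10.9 | 10.0 | LLN 10.5: (10.9 - 10.5)/0.9 = 44% | 11.0 or more |

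A Grade 2 value on an absolute cut-off is reset only if the LLN lies below the whole Grade 1 band.

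**Step 5: emergence, where that definition is applied.** Assume an ANC LLN of 1.2.
- Baseline 1.5, later 1.25: normal under the SAP; emergent Grade 1 under Attachment 1.
- Baseline 1.25, later 1.1: emergent Grade 1 under the SAP, because the baseline counts as normal; not emergent under Attachment 1, because both values are Grade 1.

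Emergent counts can therefore move either way.

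**Step 6, secondary: haemoglobin graded by decrease from baseline.** The table grades falls of 2.5 to 3.4, 3.5 to 4.4 and at least 4.5 g/dL as Grades 1, 2 and 3. The SAP bullet does not say whether it covers these. Read literally, it resets the grade whenever the later value is in range, which requires baseline >= LLN + fall.

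| Assumed LLN | Grade 1 (+2.5) | Grade 2 (+3.5) | Grade 3 (+4.5) |
|---|---|---|---|
| 11.0 | 13.5 | 14.5 | 15.5 |
| 13.5 | 16.0 | 17.0 | 18.0 |

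A Grade 3 reset, which would drop the value from the Grade 3/4 listing, needs a high baseline.

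**The case against.** The strongest defence is protocol 11.5, the section on laboratory analysis. It names the DAIDS table and the laboratory's normal ranges together, is not limited to ungraded tests, and gives neither precedence; section 11 leaves details to the SAP. On that reading the bullet supplies the missing detail. This does not hold up. A general phrase does not displace a specific clause that addresses this overlap, decides it and works an example. SAP 5.2 also already gives normal ranges their own use, for tests with no grade.

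Several limiting points do stand:
- The rule is the same in every arm and randomisation is stratified by region, so no between-arm bias is shown. Safety is descriptive. Adverse event reporting, the 48-hour repeat tests and the holding rules are unaffected.
- The WBC and platelet limits in the table have no anchor in the documents; foreseen overlap is shown only for ANC and haemoglobin.
- SAP 5.2.1 asks for worst emerging abnormalities only for ungraded tests, although the definition in 5.2 covers toxicity grades. The emergence effect is conditional on its use for graded tests.
- Attachment 1's overlap clause does not address falls from baseline, so the haemoglobin-decrease point is an ambiguity and not a contradiction of that clause.
- SAP section 1 says the Week 96 analysis is done and will not be rerun, and the extension schedule has no safety laboratory tests. The remedy has to be supplementary.

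**Conclusion.** The concern holds. SAP 5.2 departs from the protocol's grading standard for values that overlap local normal limits, and does not say so. The SAP's Appendix 1 refers back to the protocol table without exception, and its amendment history mentions only the extension data. The modifications marked in Attachment 1 as following FDA vaccine guidance concern fever and injection-site reactions, not laboratory overlap.

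The effect is confined, among the graded blood tests, to four with fixed cut-offs, and mostly to Grade 1. Depending on the local lower limit, anywhere from none to all of a Grade 1 band is reset. How many subjects that involves cannot be derived. The departure should be corrected in the reporting; it does not threaten the comparison between regimens.

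**What to change.** 1. Keep the bullet as the record of the rule used for the completed Week 96 tables, and annotate it as a departure from Attachment 1.
2. Establish and record whether those tables applied local limits to haemoglobin grades based on decrease from baseline. State in the SAP that local limits do not apply to those grades.
3. From the existing data, produce supplementary worst-grade tables and a Grade 3/4 listing graded by Attachment 1.
4. Add a count of reclassified values by test, group and region. This supplies the size that the documents cannot.
5. Document the departure in the study report.

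The cost is minor programming, with no new data and no rerun of the Week 96 analysis. Worst-grade counts may rise slightly, and readers will see two sets of laboratory tables that need a short explanation.

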### 5.2.1. **Analysis methodology**

Laboratory data will be analyzed based on the full analysis set. Unless specified otherwise, percentages are calculated versus the number of subjects in the analysis set with non-missing data for the parameter, period (if applicable) and treatment group under evaluation.

Tabulations of the worst graded abnormalities per period following vaccination will be provided. Grade 3 and 4 toxicities developed following vaccination will be listed. Tabulations of the worst emerging abnormalities (below/above) will be performed for tests that have no grading.

